## **3. Recruitment**

Principally this study will recruit from within the department of health however if needed then participants will be recruited from the University of Bath campus a by word of mouth and by poster advertisement. The full enrolment protocol is outlined below, however participation

will be centred on the provision of obtaining informed consent prior the study and throughout participation.

#### Inclusion criteria

- Body mass index 20.0-29.9 kg·m^-2
- Age 18-45 years
- Willing to abstain from food intake for just over 3 days (~82 hours)
- Able and willing to provide informed consent and safely comply with study procedures
- Females to maintain record of regular menstrual cycle phase or contraceptive use
- No anticipated changes in lifestyle during the study (e.g. holidays or exercise programmes)

#### Exclusion criteria

- Any reported condition or behaviour deemed either to pose undue personal risk to the participant or introduce bias
- Any diagnosed metabolic disease (e.g. type 1 or type 2 diabetes)
- Any reported use of substances which may pose undue personal risk to the participants or introduce bias into the experiment
- Pregnancy
- Breastfeeding
- Lifestyle not conforming to standard sleep-wake cycle (e.g. shift worker)
- History of eating disorders (e.g. anorexia)
- Any reported recent (<6 months) change in body mass ( $\pm$  3%)
- Uncontrolled hyperthyroidism
- Advanced cerebrovascular insufficiency or dementia
- Advanced liver or kidney insufficiency
- History of migraine and or headache
- Psychotic disorders
- Unstable or severe coronary artery disease
- Retinal detachment
- Duodenal or stomach ulcer
- Cancer and malignant disease
- Regular use of Non-steroidal anti-inflammatory drugs (NSAIDs)
- Use of Systemic corticoids
- Use of Antihypertensives (especially beta-blockers and diuretics)
- Use of Antidiabetics
- Use of Anti-coagulants
- Use of Psychotropics (especially neuroleptics and lithium)
- Use of Anticonvulsants.

Participants will provide informed consent both verbally and in written form. Upon expression of initial interest in the study, potential participants will be provided with the relevant appended 'Participant information sheet' to read in their own time, dependent on which phase(s) of the study they wish to take part in. Should they then decide they would like to participate in the study, they will be invited to a pre-enrolment meeting at the University, whereby a member of the research team, who is experienced in taking informed consent, will explain the study protocols and procedures. Potential participants are encouraged to ask any questions they may have, in order for them to fully understand what participating in the study

entails. Following this, if the individual is still willing to participate, they will fill out 2 copies of the appended 'Informed Consent Form' - – (V1.0 18/08/20), and eligibility screening will occur.

### 3. Confidentiality

Each participant will be allocated a unique study identification code upon enrolment to the study. This will be noted alongside their contact information in a designated file which will be kept locked in a separate office. All subsequent documents used throughout the study will be marked with this identification code rather than any identifiable information to prevent any association between personal data and recorded outcome measures by any unauthorised personnel or in any presentation of the data. Any electronic identifiable information will be kept in a password protected computer in a locked office of which only the members of the research team can access. Additionally, no identifiable information will be included in the presentation and dissemination of the results of this study.

### 4. Trial days

3 days prior to the first experimental visit participants will visit the laboratory to be fitted with a continual glucose monitor, an actiheart activity monitor, as well as a food diary and food scales. They will be asked to record energy intake and to standardise physical activity, caffeine, and alcohol intake.

Upon finishing the 3 days of lifestyle standardisation participants will enter the laboratory for where weight, height, waist:hip circumference, sagittal-abdominal diameter, and skin-fold will be assessed prior to assessment of resting metabolic rate, blood pressure and urinary ketones. Participants will also undergo grip strength, reaction time, and sensory experience assessment. Following this, samples of skeletal muscle and adipose tissue will be collected from the *vastus lateralis* and abdominal adipose tissue respectively. An intravenous cannula will then be placed a 10 mL blood samples will be drawn before ingestion of a carbohydrate rich porridge breakfast (7.3 mg carbohydrate·kJ).

A 3-hour postprandial period follows the ingestion of breakfast with blood samples will be collected at 15, 30- and 60-minute intervals during the first, second and third hour respectively alongside hourly expired gas samples and assessment of subjective appetite and mood. Upon completion of the 3-hour post-breakfast period, participants will have completed the visit and will be provided with a standardised lunch and dinner. Participants will also be provided with urinary ketone sticks, a blood pressure monitor, a set of weighing scales, as well as an actiheart monitor.

Participants will be asked to assess urinary ketones using provided assessment sticks in the evening at 2000 h.

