Surprisingly, only one study to date has investigated changes in post-prandial metabolism following mixed meal ingestion, as opposed to oral or intravenous tolerance tests [2, 9, 10]. Notably, whilst this study aimed to achieve a 72-h starve, provision of the mixed meal tolerance test immediately prior to beginning the 72-h starvation period resulted in an actual starve duration closer to ~2 days. Given the dramatic effect of acute starvation on gastric emptying [9] it is especially important to investigate the meal responses. Furthermore, given that insulin resistance following prolonged fasting persists even following a 24 h refeed, it would be insightful to include measures of sequential meals (i.e. the response to the standardised lunch and dinner will be assessed via continual glucose monitors). Finally, few, if any, studies have assessed the physical activity response to periods of prolonged fasting. Necessarily, methods such as doubly labelled water would not be appropriate due to the underlying assumptions with RQ as well as only giving a total energy expenditure value. Alternatively, employment of combined heart rate/accelerometry (Actiheart), would be appropriate in order to assess the change in physical activity levels, whilst giving a detailed breakdown in changes in intensity.

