**2.4 Study design**

This study will employ a single-arm, non-randomised design in which participants will act as their own control prior to undergoing 3 days of starvation. The control phase includes ~3 days of habitual energy balance assessment before coming into the laboratory for baseline metabolic and anthropometric assessment. Participants will be provided with monitoring equipment throughout the 3 days of starvation and will be asked to provide a blood sample as well as record their blood pressure, weight, and urinary ketones each day. On the middle day participants will also be asked to come into the lab to provide a blood sample at 2000 h.

**Figure 1.** Protocol schematic depicting the study design.

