### 5. Intervention

Participants will be provided with their last meal at ~1900 h on the day of the meal testing. From this point onwards, participants will be asked to refrain from eating for ~82 hours until their return visit to the laboratory. Throughout this period of extended fasting participants will be provided with 80 mmol sodium and 40mmol potassium daily (to consume in the form of slow-release tablets) to minimize the confounding effects of fluid deprivation and intravascular volume depletion on cardiovascular reflexes and sympathetic nervous system activity. Subjects will also be permitted to consume water, non-sugared carbonated drinks

and, with the exception of the day of the pre/post measurements, non-sugared decaffeinated coffee and tea (if they normally consume tea and coffee).

Upon waking each day participants will be asked to assess their urinary ketone levels, blood pressure, and weight. Participants will be asked to repeat this in the evening at 2000 h.

Each day participants will be asked to return to the laboratory to provide a blood sample. On the second day of starvation participants will also be asked to provide a blood sample at 2000 h.

Furthermore, throughout the intervention participants will be asked to wear an actiheart monitor in order to assess physical activity levels in response to prolonged fasting.

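### The change in Actiheart activity cannot be put down to fasting alone: the control days are described in two ways, and four laboratory visits fall in the fast against none or one in the control days

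*Combined protocol and SAP*

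**What the plan says.** Section 2.4 sets out the design: "This study will employ a single-arm, non-randomised design in which participants will act as their own control prior to undergoing 3 days of starvation". It describes the run-in as follows: "The control phase includes ~3 days of habitual energy balance assessment before coming into the laboratory for baseline metabolic and anthropometric assessment".

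Section 4 covers the same days. The Actiheart is fitted at a visit three days before the baseline test, and the instruction to participants is "They will be asked to record energy intake and to standardise physical activity, caffeine, and alcohol intake". The section then refers to the period under another name: "Upon finishing the 3 days of lifestyle standardisation participants will enter the laboratory".

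Section 2.3 gives the reason for the monitor. It says that few if any studies have looked at activity during prolonged fasting, and that "combined heart rate/accelerometry (Actiheart), would be appropriate in order to assess the change in physical activity levels". Section 5 has the monitor worn through the fast for that purpose.

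Section 5 also schedules the fasting days: "Each day participants will be asked to return to the laboratory to provide a blood sample". Sections 2.4 and 5 add a sample at 2000 h on the middle day, which Section 2.4 places in the laboratory. Section 7 confirms venepuncture on days 1, 2 and 3.

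**The concern.** A before-and-after comparison in one group isolates the intervention only if the two periods otherwise ask the same of participants. Here they may not, in two respects.

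First, it is unclear what the control days represent. If standardising means keeping to one's usual level, they are a habitual baseline. If it means holding activity to some set level, they are not. Section 5 repeats no activity instruction for the fast, so under the second meaning the two periods would run under different rules.

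Second, the protocol itself generates activity in one period that it hardly generates in the other. If fasting lowers spontaneous activity, required visits could mask part of the fall. If fasting changes nothing, they could appear as a rise. With 6 to 10 participants who all follow the same visit schedule, an offset of this kind does not average out.

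At stake is the reading of a measure that Section 2.3 presents as filling a gap in the literature.

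**Working it through.** The plan gives no figure for activity, so there is none to reproduce. The check is a count of visits, a clock calculation and a comparison of wording.

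**Which days are fasting days.** The last meal is at about 1900 h on the test day (day 0) and the fast lasts about 82 h (Section 5). 19 + 82 = 101 h after midnight at the start of day 0, and 101 = 4 × 24 + 5. The fast therefore ends at about 0500 h on day 4. Days 1, 2 and 3 are the full fasting days, and the follow-up visit falls on day 4.

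**Visits in each period.**
- Fast: 3 days × 1 daily visit + 1 evening visit on day 2 = 4 (Sections 2.4, 5 and 7).
- Control days: 0, or 1 if the fitting visit at their start is counted (Section 4).
- Imbalance: 4 − 0 = 4, or 4 − 1 = 3.
- The baseline and follow-up test visits mirror each other and are left out.

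**Possible size.** The documents give no travel time, so the active minutes per round trip, m, are an assumption. The added activity per fasting day is 4m/3. If the fitting visit is counted, the control days carry m/3 per day and the net difference is 4m/3 − m/3 = m.

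| m (min, assumed) | Added per fasting day, 4m/3 | Net of fitting visit, m |
|---|---|---|
| 0 | 0 | 0 |
| 10 | 13 | 10 |
| 20 | 27 | 20 |
| 30 | 40 | 30 |
| 60 | 80 | 60 |

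The zero row is realistic: Section 3 (Recruitment) draws mainly on the department, then on the campus, so a daytime visit may add little for someone already on site. The 2000 h visit is the likeliest real addition.

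**Wording side by side.** Section 2.4 calls the run-in habitual. Section 4 calls it lifestyle standardisation and gives an activity instruction with no level or method. The inclusion criteria ask for no anticipated change in lifestyle during the study. That fits the reading of keeping to the usual level but does not settle it.

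**Handling of visits.** Section 2.6 names no analysis of activity, and no section says how activity caused by visits will be treated.

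**The case against.** The strongest reply is about weight. Physical activity is absent from the aims and objectives (Section 2.2) and from the outcome list (Section 2.5), and Section 2.1 says that the study is not hypothesis driven. That stands: no primary or secondary conclusion is affected.

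A reader might infer that the baseline is artificial and that an activity restriction is lifted when the fast begins. The documents do not show this. The term is undefined, usual-level activity is an open reading, and silence in Section 5 does not withdraw an instruction. What stands is the inconsistency between Sections 2.4 and 4.

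A reader might also infer that the plan expects fasting to shift heart rate, and so to distort Actiheart intensity, because Section 5 mentions "intravascular volume depletion on cardiovascular reflexes and sympathetic nervous system activity". In full, that sentence explains that sodium and potassium are supplied to lessen the effects of fluid and volume loss. It describes mitigation, predicts no change in heart rate, and gives nothing from which to size one.

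Finally, the visits may add almost no activity for people who work or study on site. That stands as a limit on size. It does not remove the imbalance in the schedule, and the plan collects nothing that would show how large the effect was.

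**Conclusion.** The point holds as a limited one. Sections 2.4 and 4 describe the control days inconsistently and must be reconciled. Separately, three to four more laboratory visits fall in the fast than in the control days. In a single-arm, fixed-order design, that imbalance alone means that a change in Actiheart activity cannot be attributed to fasting alone, whatever standardising turns out to mean.

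It does not follow that the observed change would be mostly artefact, or that it would be biased in a known direction. Under the assumed 0 to 60 active minutes per round trip, the addition is 0 to 80 minutes per fasting day (0 to 60 net of the fitting visit), and the documents cannot narrow that range. The conclusion rests on the visit count and on taking the run-in days as the comparator for activity; the plan implies this by having the monitor worn in both periods but does not state it. The measure is exploratory, so the change is worth making mainly because it is cheap.

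**What to change.** 1. In Section 4, state that standardising physical activity means keeping to the usual level and recording it, in line with Section 2.4. Use the same definition wherever the activity comparison is described.
2. Have participants log laboratory visit and travel times in both periods, including the fitting visit. In Section 2.6, specify the activity comparison twice: over all hours, and with the logged windows and the same clock hours in the other period excluded.

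Reporting accelerometer counts beside heart-rate-based intensity is optional.

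The cost is a short participant log, some added wording and slightly less monitoring time in the restricted comparison. The run-in should not be shortened or loosened for this purpose: it precedes the visit that supplies the baseline for the primary outcomes, and giving up control there to serve an unlisted measure is a poor trade. The exclusion removes the visit artefact only; other differences tied to the fixed order remain and should be acknowledged when the activity result is reported.

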## **2.5 Outcome measures**

### *Primary*

Metabolic response to feeding before and after a prolonged fast  
Change in amino acid metabolism (i.e. BCAAs and ketoacids) in skeletal muscle, adipose tissue, and in the circulation

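### The readable text does not secure a standardised overnight-fasted baseline, so avoidable noise enters both primary outcomes; a provided dinner the evening before would fix this cheaply

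*Combined protocol and SAP*

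**What the plan says.** All references are to the combined protocol and SAP.

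- **Reference state.** Section 2.4 is a single-arm design in which "participants will act as their own control prior to undergoing 3 days of starvation". Baseline is therefore the only comparator for both primary outcomes in section 2.5: "Metabolic response to feeding before and after a prolonged fast", and the change in amino acid metabolism in muscle, adipose tissue and blood.
- **Run-in diet.** Section 2.4: "The control phase includes ~3 days of habitual energy balance assessment before coming into the laboratory for baseline metabolic and anthropometric assessment". Section 4 supplies a food diary, food scales, a glucose monitor and an activity monitor, and then says: "They will be asked to record energy intake and to standardise physical activity, caffeine, and alcohol intake".
- **Baseline visit.** Section 4: "Upon finishing the 3 days of lifestyle standardisation participants will enter the laboratory for where weight, height" and other body measurements are taken. Resting metabolic rate, both biopsies, the pre-meal blood sample and the porridge meal test follow. No clock time or fasting requirement appears.
- **Start of the long fast.** After the baseline test, section 4 provides a standardised lunch and dinner. Section 5 fixes the time: "Participants will be provided with their last meal at ~1900 h on the day of the meal testing", followed by ~82 h without food.
- **Follow-up.** Section 6 repeats the baseline visit, again without a start time.
- **Analysis.** Section 2.6 plans repeated-measures ANOVA and paired tests. It names no adjustment for hours fasted or previous intake.

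**The concern.** One end of the within-person comparison is anchored to a provided meal, a clock time and an approximate duration. The other end has none of these in the text. Participants may arrive at baseline after evening meals that differ in size, composition and timing.

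The measurements taken at that visit (pre-meal amino acids in blood and tissue, resting metabolic rate, and the response to a test meal) are ones on which recent intake can plausibly act. Section 2.3 itself argues that adipose metabolism shifts early in a fast, by about 20 h. That supports the principle that hours since eating matter, although it does not show a difference within the range of ordinary overnight fasts.

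Two things are at stake. One is precision: noise at baseline passes undiluted into each participant's change score, in a sample of only 6-10. The other is definition: a report could not state how many hours fasted the before state represents, unless this is recovered afterwards.

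**Working it through.** **1. The plan's own figure.** The sample size of 6-10 (section 2.6) cannot be reproduced. No alpha, power, effect size, standard deviation or within-person correlation is given, so the effect of baseline noise on power cannot be derived from the documents either.

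**2. The two visits side by side.**

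| Item | Before baseline | Before follow-up |
|---|---|---|
| Last meal | habitual, recorded | provided, standardised dinner |
| Time of last meal | not stated | ~1900 h |
| Fasting interval | not stated | ~82 h |
| Visit start time | not stated | not stated |

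**3. Clock arithmetic.** From section 5, 1900 h + 82 h = 0500 h on the fourth morning. With assumed visit starts of 0700, 0800, 0900 and 1000 h, the fast would be 84, 85, 86 and 87 h. The last-meal time, the ~82 h and the unstated start time should be reconciled.

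**4. Spread of the fasting contrast (assumed times).** Take both visits at 0800 h, and last food before baseline between 1800 h and 2300 h.

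- Baseline fast: from 24 − 18 + 8 = 14 h down to 24 − 23 + 8 = 9 h, a spread of 5 h.
- Follow-up fast: 85 h.
- Contrast: 85 − 14 = 71 h up to 85 − 9 = 76 h.
- With a 1900 h dinner before baseline: baseline fast 13 h, contrast 85 − 13 = 72 h for everyone.

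**5. Effect on the paired change (assumed variances).** Let v be the variance at each visit and ρ the within-person correlation. Let the uncontrolled evening add independent noise k·v at baseline.

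Var(change) = 2v(1 − ρ) + k·v, so the relative increase is k / [2(1 − ρ)].

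With ρ = 0 (equal, independent visit variances):
- k = 0.10: 0.10 / 2 = 5%. Effective n is 6/1.05 = 5.7 or 10/1.05 = 9.5, a loss of 0.3 or 0.5 participants.
- k = 0.30: 0.30 / 2 = 15%. Effective n is 6/1.15 = 5.2 or 10/1.15 = 8.7, a loss of 0.8 or 1.3.
- The standard deviation of the change rises by √1.05 − 1 = 2.5% to √1.15 − 1 = 7.2%.

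With ρ = 0.5, also assumed, the denominator is 1 and the increase is 10% to 30%:
- n = 6: 6/1.10 = 5.5 to 6/1.30 = 4.6, a loss of 0.5 to 1.4.
- n = 10: 10/1.10 = 9.1 to 10/1.30 = 7.7, a loss of 0.9 to 2.3.

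Neither k nor ρ comes from the documents. The calculation shows how baseline noise passes into the change; it does not estimate how much there is.

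**The case against.** The strongest reply is that the baseline visit is plainly meant to be a fasted morning visit. Resting metabolic rate comes first, blood is drawn before eating, and the test meal is called a breakfast. Figure 1 and the appended participant information sheet, either of which could tell participants to arrive fasted, are not available for this review. This stands. A reader might infer that baseline is not overnight-fasted, and the documents do not support that. The text is silent on the interval, and silence is not a fed baseline.

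Second, intake before baseline is not unknown. It is weighed and recorded while glucose is monitored, so the last meal, and perhaps its time, may be recoverable. This also stands, but it allows description afterwards more than correction: no adjustment is planned, and 6-10 people would support little.

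Third, habitual intake in the run-in is a stated choice in exploratory work without a hypothesis (section 2.1), and a contrast of over 70 h may dwarf a few hours' variation. That is likely for responses as large as ketones. It is less certain for amino acids and the meal response, which are the primary outcomes.

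A reader might also think the protocol contradicts its own rationale, because section 2.3 criticises an earlier mixed-meal study on fasting time: "provision of the mixed meal tolerance test immediately prior to beginning the 72-h starvation period resulted in an actual starve duration closer to ~2 days". It does not. That criticism concerns a shortened long fast, and section 5 answers it by counting from the evening meal after the test. It says nothing about control of intake before baseline.

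**Conclusion.** The point holds as a cheap improvement. The readable text does not specify or secure a standardised overnight-fasted baseline, and that visit is the sole reference for both primary outcomes. The consequence is avoidable between-person noise in each paired change and a loosely defined before state.

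It should not be read as a finding of bias. Nothing in the documents suggests that baseline fasts would be systematically short or long, or that the composition of a meal some 82 h earlier affects the follow-up measurements. The difference in fasting length between visits is the intervention itself.

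The size is unknown. Under the assumed 10% to 30% rise in baseline variance with equal, independent visits, the variance of the change rises by 5% to 15%, equivalent to losing 0.3 to 0.8 of 6 participants or 0.5 to 1.3 of 10. Positive within-person correlation would make the relative loss larger. The conclusion concerns the text only; a fasting instruction in Figure 1 or the information sheet would narrow it to the content of the last meal and whatever timing was still left open.

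**What to change.** In section 4, provide the same standardised dinner used on the meal-test day, to be eaten at ~1900 h on the evening before the baseline visit, with only water afterwards. State one visit start time and use it at both baseline and follow-up. Record the actual hours since last food at both visits and report them. The contrast then becomes a known overnight interval against the long fast, after the same last meal. The fasting intervention itself is unchanged.

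The cost is one extra dinner per participant (6-10 meals), which could be handed out at the existing fitting visit, plus a sentence or two of text and one recorded item per visit. The downside is that the last evening of the three-day food record is no longer habitual, so habitual intake would be averaged over the remaining run-in meals.

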### *Secondary*

Change in circulating glycerol and FFAs across the prolonged fast (indices of lipolysis from adipose tissue)

Change in Autophagy (in skeletal muscle and neutrophils)

Total nitrogen (or at least urea nitrogen) in urine (24h collection) throughout the fast (or at least 1st vs last day)

Change in plasma lactate and pyruvate in response to prolonged fasting (indices of Cori cycle)

Change in urinary (acetoacetate), and circulating (beta-hydroxybutyrate) ketones in response to prolonged fasting.

Change in body mass, pre-post, and during the prolonged fast.

Change in blood pressure pre-post, and during the prolonged fast.

Change in waist-hip circumferences pre-post the prolonged fast.

Change in sensory experience (pain, fatigue, drive) in response to prolonged fasting.

Change in haematocrit/haemoglobin pre-post the prolonged fast.

Change in grip strength pre-post the prolonged fast.

Change in reaction time pre-post the prolonged fast.

Change in aspects of immune function and infection risk

Change in interstitial fluid glucose concentrations pre-, post-, and during the prolonged fast (assessed via continual glucose monitoring)

Occurrence of adverse events (e.g. nausea, vomiting, migraines)

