## **6. Follow up visit**

Upon completion of the intervention, participants will visit the laboratory at the University of Bath, and repeat the pre-intervention visit with the porridge breakfast. Following this repeated visit, participants will again be provided with a standardised lunch and dinner.

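### No familiarisation is specified for reaction time or grip strength, so any first-to-second-test gain cannot be separated from the fasting effect on these two secondary outcomes

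*Combined protocol and SAP*

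**What the plan says.** Section 2.5 lists both tests as secondary pre-post outcomes; for reaction time the entry is "Change in reaction time pre-post the prolonged fast". Section 4 (Trial days) places the first listed administration at the baseline laboratory visit: "Participants will also undergo grip strength, reaction time, and sensory experience assessment". Section 6 (Follow up visit) has participants return after the fast and "repeat the pre-intervention visit with the porridge breakfast", which is the second administration. With about 82 hours of fasting starting on the evening of the baseline day, the two sessions are roughly four days apart.

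Two earlier contacts are described. At the pre-enrolment meeting (end of section 3, Recruitment), a team member "will explain the study protocols and procedures", after which consent and eligibility screening follow. Then, in section 4, "3 days prior to the first experimental visit participants will visit the laboratory to be fitted with a continual glucose monitor, an actiheart activity monitor", with a food diary and food scales. Neither contact lists a performance test or practice. No device, number of attempts or scoring rule is given for either test.

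Section 2.4 gives the design: "This study will employ a single-arm, non-randomised design in which participants will act as their own control prior to undergoing 3 days of starvation". Section 2.6 assigns variables measured only before and after the fast to a paired t-test or Wilcoxon test, with no term for order or practice, and plans 6 to 10 participants.

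**The concern.** People often do better on a performance test the second time, once they know the task. Here every participant has the fasted test second, and nobody repeats the tests without fasting. Using participants as their own controls removes differences between people but not a change that comes from repetition. The three-day control phase does not help either: it covers habitual energy balance and does not repeat these tests, so it gives no estimate of test-retest change.

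What is at stake is how two functional outcomes are read. If fasting slows reactions and repetition speeds them, the two partly cancel and the fast may look neutral. If fasting does nothing, a repetition gain may be reported as a fasting benefit. Blood, tissue and body-size measures in the same paired analysis have no comparable learning component.

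**Working it through.** **Plan's own figure.** The sample size of 6 to 10 (section 2.6) rests on previous research. No effect size, SD, alpha, power or dropout is given, so it cannot be reproduced, and it was not derived from these two tests.

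**Structure.** Score each test so that higher is better, and let D = post minus pre for one participant. Let F be the fasting effect (negative for a decline) and L the gain from first to second test. Then E(D) = F + L. With two observations per person, one arm and one order, only the sum can be estimated. If L is as large as the decline, E(D) = 0, and a significant decline appears with probability 0.025 whatever the sample size.

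**Illustration of size.**
- From the documents: n = 6 to 10; paired t-test.
- Assumed, because the documents are silent: two-sided alpha 0.05; gains L of 0, 0.1, 0.3 and 0.5; a true decline of 1.0. All effects are in units of the SD of D, which is held constant.

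For standardised mean change δ, the paired t statistic follows a noncentral t distribution with n − 1 degrees of freedom and noncentrality δ√n. The critical values are 2.571 (n = 6) and 2.262 (n = 10).

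*False-change rate*: no fasting effect, so δ = L; probability that |t| exceeds the critical value. Example, n = 10 and L = 0.3: noncentrality 0.3 × √10 = 0.949, giving 13.6%.

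*Power*: true decline 1.0, so the net decline is 1.0 − L; probability of a significant decline. Example, n = 10 and L = 0.3: net 0.7, noncentrality 0.7 × √10 = 2.214, giving 50.6%.

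| Assumed gain L | False change, n = 6 | False change, n = 10 | Power, n = 6 | Power, n = 10 |
|---|---|---|---|---|
| 0 | 5.0% | 5.0% | 51% | 80% |
| 0.1 | 5.5% | 5.9% | 43% | 72% |
| 0.3 | 9.3% | 13.6% | 29% | 51% |
| 0.5 | 17.1% | 29.3% | 17% | 29% |

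The false-change rate rises with n because the test becomes better at detecting a shift that is real but is not due to fasting. A larger sample therefore does not cure the problem.

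**The case against.** **The plan is silent; it does not exclude practice.** A reader might infer that participants certainly meet both tests for the first time at baseline. The documents do not support that. Section 4 gives the tests one short sentence, and practice attempts within the visit or a demonstration at the pre-enrolment meeting are neither specified nor ruled out. What stands is that none is specified, so following the plan as written leaves the confound in place.

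**The size is assumed.** The documents give no practice gain, SD or effect size. At a gain of 0.1 SD the false-change rate barely moves, and at zero there is no problem. A reader might infer a demonstrated, large bias; the table shows only what follows if gains of that size occur.

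**The two tests differ.** Nothing supports an equal gain for both. Learning is more plausible for reaction time than for grip. If grip depends on effort, motivation after a long fast is a separate matter that practice would not settle.

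**No direction is stated.** It is tempting to say that learning runs against a harm the protocol expects. Section 2.1 says the research is not hypothesis driven, and section 2.5 lists only change. Masking a decline and mimicking an improvement are both possibilities, not predictions of the plan.

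**The outcomes are minor and already imprecise.** They are two of fifteen secondary entries and appear in neither the aims nor the objectives. Even without learning, the decline detectable with 80% power is 1.43 SD at n = 6 and 1.00 SD at n = 10, so a null result would say little anyway. This limits the importance of the point. It does not remove it, because low power does not explain away a significant improvement produced by repetition.

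**Conclusion.** The point holds as a limited design confound. As written, the paired comparison for reaction time, and less convincingly for grip strength, estimates the fasting effect plus any first-to-second-test gain, and no analysis of these data can split the two. That conclusion needs no numerical assumption.

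The size does. Across assumed gains of 0 to 0.5 SD, the consequences run from none to a false-change rate of 17% (n = 6) or 29% (n = 10). At a gain of 0.3 SD, power for a true 1.0 SD decline drops by 22 percentage points at n = 6 (51% to 29%) and 29 at n = 10 (80% to 51%). These figures also assume a paired t-test at two-sided 0.05.

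A reader might extend this to the trial's main findings. The documents do not support that: the primary outcomes are the metabolic response to feeding and amino acid metabolism, which do not depend on practice at a task. This is a cheap improvement to two secondary outcomes, not a threat to the study.

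**What to change.** In section 4, add a short unscored familiarisation block, chiefly for reaction time and also for grip strength, to the laboratory visit three days before baseline. State the number of practice trials, discard their results, and specify the same fixed number of scored trials and the same scoring rule at the pre and post visits. If practice already takes place informally, writing it down makes it uniform.

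In section 2.6 and in the report, state that residual practice effects cannot be excluded in a single-arm, fixed-order design, so a null or improved result on these two tests is not evidence that fasting has no effect.

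The cost is a few minutes per participant at a visit already scheduled, and the test equipment must be available at that visit, where the plan does not currently list it. One session reduces learning but may not remove it, which is why the reporting statement is needed as well. The block must be in place before a participant's first scored test. For anyone already tested at baseline without practice, only the reporting statement remains.
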